On Day 18, blood sampling for haematology lab test shall be repeated

NOTE:

Ophthalmic or dermatological visits shall be performed and repeated bi-weekly in case of ocular or dermatological events higher than grade 1 during the study treatment period. The frequency of ophthalmic and dermatological visits can be increased upon Investigator's judgment.

CYCLE 2

Visit 1 (Day 1-Day 4)

Study drug administration will be performed as inpatient treatment. In addition starting from Cycle 2, hospitalization is not mandatory if the patient did not experience any infusion reactions or any adverse events during the administration at Cycle 1.

Day 1

Prior to study drug administration

- Physical examination including vital signs
- ECOG PS evaluation
- Weight measurement
- 12-lead ECG record
- Blood sampling and urine collection for safety lab tests, including β -HCG pregnancy testing

NOTE: safety laboratory tests performed within 24 hours prior to Day 1 are accepted and do not need to be repeated at Visit 1 (Day 1) prior to study drug administration.

- PK blood sampling (pre-infusion)
- Blood sampling for immunogenicity assessment
- Blood sampling for free CD205 assessment
- TLS prophylaxis if applicable (see Appendix II)
- Premedication
- Recording of AEs and change in concomitant medication

Study drug administration

- Study drug administration, given as a 3-hour IV infusion
- Vital signs every 30 minutes during the first hour of study drug administration and then at every hour until the end of infusion. In case of temporary infusion interruption, vital signs should be collected every 15 minutes until the first hour post-infusion re-start and then every hour until the end of infusion (or until 1-hour after the permanent infusion interruption)
- Continuous ECG monitoring during the IV infusion up to 30 minutes after end of infusion and 12-lead ECG record at 30 minutes after end of infusion

NOTE: If ECG monitoring equipment is not available, heart rate should be monitored up to 30 minutes after the end of infusion with final 12-lead ECG record at 30 minutes after the end of infusion.

- PK blood sampling at the end of infusion, and at 1, 2, 4, 6, 8, 10, 12, and 16 hours after the end of infusion

NOTE: PK blood sampling at 10, 12 and 16 hours after the end of infusion is not mandatory

Day 2, Day 3, and Day 4

Post study drug administration

- Physical examination, including vital signs
- Blood sampling and urine collection for safety lab tests

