- The total dose calculated for the first study drug administration has to be also applied for the following ones, provided that the actual patient's weight is within \pm 10% of the weight measured prior to the first study drug administration; otherwise, the total dose to be given shall be calculated based on the weight measured at the corresponding visit.
- The administration of the study drug should only be carried out in a facility in which resuscitation equipment and medical personnel trained in the treatment of anaphylaxis and TLS are immediately available.
- Starting from Cycle 3, the dose of dexamethasone can be adjusted upon Investigator's judgment.
- Starting from Cycle 2, blood sampling for haematology lab test at Day 11 and Day 18 shall be performed if clinically needed.
- If any interruption occurs during MEN1309 infusion at any cycle, an additional blood sampling for PK will be taken at the time of each infusion interruption and just before each infusion resumption.
- ONLY for dose levels higher or equal to 0.8 mg/kg, PK blood samples will be taken at Visits 2 and 3 of each cycle in conjunction with safety blood samples; in case additional samples will be required between study visits for safety reasons, an additional PK sample will be collected.

End of Study Visit (within 6 weeks after the last administered dose or at the time of study withdrawal/treatment discontinuation of study drug)

- Tumor assessment using RECIST v1.1 for Step 1 based on CT scan or MRI and NHL assessment using Cheson Criteria (The Lugano Classification, 2014) for Step 2 based on CT/(PET)-CT scan or MRI
- Physical examination and vital signs
- 12-lead ECG record
- ECOG PS evaluation
- Blood sampling and urine collection for safety lab tests, including β -HCG pregnancy testing
- Blood sampling for immunogenicity assessment
- Blood sampling for free CD205 assessment
- Recording of adverse events and change in concomitant medications

NOTE:

All patients shall undergo the End of Study Visit at the scheduled date within 6 weeks after the last administered dose or at the time of study withdrawal/treatment discontinuation of study drug. Unscheduled assessments showing disease progression and leading to patient's withdrawal can replace the End of Study Visit provided that all assessment/procedures scheduled for this Visit are completed.

Survival Follow-up (up to a period of 12 months after last patient in)

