Demographic and baseline characteristics, including age, gender, race will be summarized by cohort. All demographic data recorded on the eCRF will be listed.

Medical History and Concurrent Medical Conditions

Medical history will be coded using the Medical Dictionary for Regulatory Activities (MedDRA version 15.1). The number of patients with at least one recorded medical history or current medical condition will be presented using frequency counts and percentages as well as an incidence table by System Organ Class (SOC) and Preferred Term (PT). The safety population will be used for this summary. Details of medical history will be provided in listings.

Safety Analyses

Safety evaluations will be performed using the safety population.

Adverse Events

AEs will be categorized as Treatment-Emergent Signs and Symptoms (TESS) or Non-TESS for each of the study periods defined below. If an AE occurs for the first time or if it worsens in terms of seriousness or severity after the first study drug intake, it will be classified as TESS, otherwise it will be classified as non-TESS. Each adverse event will be classified according to the grade (Grade 1 to 6) depending on severity of the event, as specified in Section 8.6.1.5 of the Study Protocol.

The following periods are defined for assignment of TESS:

- Cycle 1: date of the administration to the day before the administration of Cycle 2 or, if the subject is discontinued, until the end of study.
- Cycle n: date of the administration to the day before start of Cycle n+1.

The following rule will be applied for each period: Period start date \leq AE start date \leq Period stop date.

The maximum relationship to study drug will be reported for the respective summaries. All AEs summaries will be based on the Safety population.

In particular grade ≥ 2 ADR will be listed since the occurrence of grade ≥ 2 ADR is associated with the switch from an ATD design to a 3+3 design.

The intensity of an adverse event is reported on the eCRF using the following definitions:

- **Mild:** It does not interfere with routine activities;
- **Moderate:** It interferes with routine activities;
- **Severe:** It makes it impossible to perform routine activities.

The maximum intensity will be used for the summaries; all events will be included in the listings.

Missing intensity will be left as missing and categorised as such.

Serious Adverse Events (SAEs) are defined in Section 8.6.3 of the Study Protocol

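### From Cycle 2 on, the SAP's date-only period rule places adverse events that begin on a dosing day before the infusion in the new cycle, one cycle late

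*SAP*

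**What the plan says.** SAP section 6.1.1.2, under Adverse Events, sets the periods for tabulating treatment-emergent events (TESS). The first is "Cycle 1: date of the administration to the day before the administration of Cycle 2", or runs to the end of study if the patient discontinues. The later ones are "Cycle n: date of the administration to the day before start of Cycle n+1". The allocation test is introduced by "The following rule will be applied for each period": an event belongs to the period whose start and stop dates enclose its start date. No clock time and no pre-dose indicator is used.

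The only before-or-after-dose test in that section is in the TESS definition. It covers an event that is new, or "if it worsens in terms of seriousness or severity after the first study drug intake". It refers to the first dose of the study, not to the dose of each cycle.

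Protocol section 8.5.1 lists the Day 1 procedures of Cycle 2 that come before the infusion. They include physical examination, ECOG status, ECG, "Blood sampling and urine collection for safety lab tests, including" a pregnancy test, and "Recording of AEs and change in concomitant medication". Cycles 3 and later repeat the Cycle 2 procedures apart from PK sampling. Laboratory tests from the 24 hours before Day 1 may stand in for the Day 1 draw.

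The SAP then builds its TESS overview, its tables by system organ class and preferred term, and the matching drug-related tables for each period, with a further summary by period and grade.

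**The concern.** Day 1 of a cycle is also the last scheduled look at the cycle before it. Something that starts on that morning, before the infusion, can only reflect doses already given. A rule that opens the new period at the calendar date of dosing puts that event in the new cycle.

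The routine schedule makes such dating plausible. Chemistry has no scheduled draw between Day 15 and the next Day 1. For haematology the protocol says "Starting from Cycle 2, blood sampling for haematology lab test at Day 11 and Day 18 shall be performed if clinically needed", so from Cycle 2 the same gap applies unless an extra draw is made. A laboratory finding dated by its sample can then carry the dosing date as its start date.

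At stake is the reading of toxicity by cycle. The plan itself distinguishes cycles: escalation rests mainly on Cycle 1, and later cycles are considered in addition (SAP section 5.1.1.1). A column headed Cycle 1 that loses its last events to Cycle 2 understates the first and overstates the second.

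**Working it through.** The plan gives no figure to reproduce. The check applies the SAP's rule to cases and compares the assigned period with the number of doses actually received at onset.

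**Inputs**
- Period k: start = date of dose k; stop = date of dose k+1 minus 1 day (SAP 6.1.1.2).
- Allocation: start date of period ≤ AE start date ≤ stop date of period (SAP 6.1.1.2).
- Dosing interval: at least 21 days, with up to 3 days' allowance (Protocol 8.5.1). Intervals of 21, 24 and 28 days were tried; 28 stands for a 7-day delay.
- Assumption: onset 2 hours before or after the infusion, on the same date.

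**Results**

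| Recorded onset | Doses received | SAP period | Agree? |
|---|---|---|---|
| Day before dose 2 | 1 | Cycle 1 | yes |
| 2 h before dose 2, same date | 1 | Cycle 2 | **no** |
| 2 h after dose 2 | 2 | Cycle 2 | yes |
| 2 h before dose 3, same date | 2 | Cycle 3 | **no** |
| Day 22, dose 2 then held 7 days | 1 | Cycle 1 | yes |
| Day 22, dose 2 never given | 1 | Cycle 1 | yes |

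The first four rows are the same at all three intervals. Dose 2 falls on study Day 22, 25 or 29, and dose 3 on Day 43, 49 or 57.

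At the 21-day interval, the event in the second row starts 21 − 2/24 = 20.9 days after dose 1. By elapsed time it lies within 21 days of the first dose, yet it is tabulated under Cycle 2.

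**Cycle 1 Day 1.** An event starting 2 hours before dose 1 meets the Cycle 1 date test with no dose received. Here the TESS definition intervenes: a new event before the first intake is non-TESS. No equivalent clause exists for dose 2 onward.

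**With the boundary at infusion start.** The second row moves to Cycle 1 and the fourth to Cycle 2. No other row changes.

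**The case against.** The strongest reply is that the rule uses the event's start date, not the date of discovery. A symptom reported on the morning of Day 1 but dated two days earlier stays in the right cycle. So does an abnormality from a draw on the day before. A finding serious enough to delay or cancel the dose also stays, because the new period does not open that day. All of this stands. It leaves mainly findings dated by the Day 1 pre-dose sample or examination that did not hold the dose, and the documents do not say how laboratory events are dated.

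The second reply is that little depends on these periods. DLTs are judged against the protocol's criteria and reviewed by the Cohort Review Committee (Protocol 8.5.5.1 and 8.7). Relatedness is to the study drug, not to a particular dose. Laboratory data are also listed and summarised by visit, so the Day 1 values remain visible. The protocol's own safety analysis (9.3.4) does not ask for by-cycle tables. This also stands, and it limits the consequence to the by-period tables. It does not make those tables right.

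Three stronger readings are tempting, and the documents do not support them.
- A reader might infer that pre-treatment findings enter Cycle 1 as treatment-emergent. The TESS definition excludes new events before the first intake. At most, a program that sees only dates needs to be told how to apply it.
- A reader might infer that the DLT count or MTD is distorted. Neither is defined by these periods, and the DLT summary is not stated to be by period.
- A reader might size the shift from the sampling gap. With dosing every 21 days, the gap from Day 15 to Day 22 is 7 of 21 days. That is a share of days under evenly spread onset, not a share of adverse events. Only clinically relevant laboratory abnormalities become events (Protocol 8.6.4), and the observed neutropenia nadir is Day 15 (Protocol 6.3), which does not fit even onset. Nor is it a ceiling: dosing 3 days late makes it 10 of 24.

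**Conclusion.** The point holds in a narrow form. From Cycle 2 on, an event dated on the dosing day that began before the infusion is tabulated one cycle late, and nothing in the SAP corrects it. The misplacement always runs towards the later cycle. It affects the by-period TESS and drug-related TESS tables, including the split between Cycle 1 and Cycle 2.

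Cumulative counts by cohort do not change, and dose-escalation conclusions are untouched. The number of events affected cannot be computed, because the documents give no count of Day 1 pre-dose events and do not state how their start dates are set. The conclusion rests on reading the period rule literally, as a program would, and on at least some events carrying the dosing date as their start date.

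**What to change.** In SAP section 6.1.1.2:
- End each cycle period at the start of the next infusion. Infusion start and end times are already recorded (Protocol 8.4.4).
- Assign a dosing-date event documented as starting before the infusion to the previous cycle. Include events identified from that day's pre-dose sample or examination.
- For Cycle 1 Day 1, state that the existing first-intake test in the TESS definition governs same-day events.
- Collection of AE onset time is not stated. Where timing relative to the infusion cannot be established from the pre-dose assessment or a before-infusion flag, keep the current date rule and footnote the table.

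The cost is a short SAP amendment and a small programming change, plus one eCRF field if a before-infusion flag is added. Some same-day events will stay unresolved, which is why the footnote is needed.

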A Treatment-Emergent SAE is defined as a TESS event classified as serious.

An AE will be classified as related to study drug if causality was recorded as “certainly related”, “probably related”, “possibly related”, “unassessable/unclassifiable”. Missing causality will be considered as related.

An overview of TESS will be provided with the number and percentage of patients reporting an event by cohort and overall for each period. The summaries will be presented for the following categories:

- Any TESS

- Any TESS by grade (<2, >=2)
- Any Serious TESS
- Any mild/moderate/severe TESS
- Any TESS leading to study drug discontinuation
- Any TESS leading to temporary study drug administration interruption
- Any related TESS (by categories)

If a patient has more than one occurrence of a TESS, the patient will be counted only once within that preferred term. The same applies to serious TESSs and drug-related TESSs.

Additionally, the following summaries of TESSs expressed as number and percentage of patients with TESSs will be presented by SOC and PT by cohort and overall, for each period:

- TESS
- Serious TESS
- Serious TESS resulting in death
- TESS of Grade >=2
- TESS of Grade <2
- TESS by intensity (by categories)
- TESS leading to study drug discontinuation
- Serious TESS leading to study drug discontinuation

Drug-related TESSs will be summarized in the same way that TESS as it is described above.

Moreover, the following summary will be presented for drug-related TESS:

- Number of events, number of patients and percentage of patients with DLT by SOC and PT

In the final TFL a summary of TESSs by period and Grade will be reported.

All adverse events (including non-TESS or AEs happening after End of Study Visit of the patient) recorded on the eCRF will be listed. A separate list of serious adverse events will be provided. TESS will be flagged in the listings.

Laboratory data

All laboratory data will be listed.

Clinical chemistry, haematology and urinalysis parameters will be summarized by parameter, visit and cohort using descriptive statistics. The change from baseline will be summarized for each post baseline visit with descriptive statistics by cohort and visit.

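### The SAP counts worsening AEs as treatment-emergent but assigns them to cycles by start date alone, so a pre-dose AE that worsens on drug has no cycle unless the worsening is a new record

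*SAP*

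**What the plan says.** All the rules are in the adverse-event part of SAP section 6.1.1.2.

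- **Treatment emergence.** New onset qualifies, and so does worsening: "if it worsens in terms of seriousness or severity after the first study drug intake, it will be classified as TESS".
- **Placement in a cycle.** "The following rule will be applied for each period": the AE start date must lie between the period's start and stop dates. No date of worsening enters the rule.
- **Periods.** The first begins on the day of the Cycle 1 administration. Later ones follow the same pattern: "Cycle n: date of the administration to the day before start of Cycle n+1". There is no pre-dose period.
- **Intensity.** After defining mild, moderate and severe, the SAP adds: "The maximum intensity will be used for the summaries; all events will be included in the listings".
- **Grade.** Each AE receives a grade. Nothing is said about a grade that changes over time.
- **Output.** The TESS overview and the tables by system organ class and preferred term are produced for each period, including splits by grade and by intensity. Drug-related TESS are summarised in the same way. In addition: "In the final TFL a summary of TESSs by period and Grade will be reported".

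Protocol section 8.6.2 has AEs assessed from the signing of consent, and the flow chart in protocol section 2.2 shows AE recording at the Screening Visit (Day -27 to Day -1). AEs with a start date before the first dose can therefore exist.

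**The concern.** Two stated rules do not fit together. The definition of TESS admits an event because of something that happens after its start date, and the period rule then looks only at the start date. For an event already present before Day 1, the two rules give opposite answers: it is treatment-emergent, but it falls in no treatment period.

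A related gap affects events that start on treatment and get worse in a later cycle. The SAP does not say in which cycle the worsening counts, or whether the maximum is taken per record, per patient and preferred term, or per period.

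The toxicity profile is a secondary objective, and timing by cycle is part of it: SAP section 5.1.1.1 says that DLT-type toxicities seen in Cycle 2 or later are also taken into account in assessing toxicity and defining the MTD. Two programmers working from this text could produce different by-cycle tables from the same data.

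**Working it through.** The plan has no figure to reproduce here. The check applies the SAP's own period rule to two hypothetical events.

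**Inputs.** Cycles last 21 days (SAP section 1). If dosing is on schedule, cycle k runs from study day 21(k - 1) + 1 to study day 21k. That gives Days 1 to 21 for Cycle 1, Days 22 to 42 for Cycle 2 and Days 43 to 63 for Cycle 3. The rule is: period start ≤ AE start ≤ period stop.

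**Events (illustrative, not from the documents).** Event A is mild from Day 10, moderate from Day 30 and severe from Day 50. Event B is mild from Day -10 and severe from Day 5.

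| Event and recording | Record start dates | Test against the periods | By-cycle table shows |
|---|---|---|---|
| A, one record holding the peak | Day 10 | 1 ≤ 10 ≤ 21 | Severe in Cycle 1, nothing later |
| A, new record at each worsening | Days 10, 30, 50 | 1 ≤ 10 ≤ 21; 22 ≤ 30 ≤ 42; 43 ≤ 50 ≤ 63 | Mild in Cycle 1, moderate in Cycle 2, severe in Cycle 3 |
| B, one record | Day -10 | -10 < 1, so no period is met | TESS by definition, in no cycle |
| B, new record at worsening | Days -10, 5 | Day -10 record is not TESS; 1 ≤ 5 ≤ 21 | Severe TESS in Cycle 1 |

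Both effects appear with one record per event and both vanish with a new record at each worsening. The recording convention therefore decides the matter, and neither document states it in general. Protocol section 8.6.4 says that clinically relevant worsening of a known laboratory abnormality should be reported as an AE; it does not cover other events.

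The two single-record results do not rest on equal ground. For B, one record is enough: the start date alone excludes it. For A, absence from later cycles also needs only one record, but showing it as severe in Cycle 1 further requires that the maximum be taken over the whole event.

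**What one lost event does to a table.** Taking patients treated in the cohort as the denominator (an assumption), one uncounted patient changes a percentage by 1/3 = 33 points in a cohort of 3, 1/6 = 17 points in a cohort of 6, and 1/25 = 4 points in the TNBC expansion of 25. How many such events there are cannot be derived from the documents.

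**Is there another table that would catch event B?** Apart from the DLT summary, SAP section 6.1.1.2 names no TESS table pooled over cycles. The list in SAP section 8.1.1.3 has no content in the copy reviewed, so a pooled table may be listed there.

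**The case against.** The strongest reply is that recording conventions belong in the eCRF Completion Guidelines (protocol section 10.1.1), which are not among these documents, and that a new record at each worsening would remove the problem. The one instruction on the subject, for laboratory abnormalities, points that way. It covers neutropenia, which protocol section 6.3 names as the most frequent adverse reaction. This stands as a limit on the point. It does not settle it: the instruction does not reach non-laboratory events, and the TESS definition speaks of an event that worsens, which reads as one continuing event.

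It can also be said that few events are exposed to the pre-dose gap. Conditions present before the study are medical history (protocol section 8.5.4.1), and patients with grade 2 or higher neuropathy, corneal disorders or uncontrolled skin disease are excluded. That is fair. Nothing in the documents shows that worsening of pre-dose AEs is common.

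A reader might infer more: that the SAP grades every AE at its lifetime maximum, so that Cycle 1 toxicity is overstated and cumulative toxicity hidden. The text does not support this. The words do not say over what the maximum is taken. With patients counted once per preferred term and tables made for each period, it may mean the highest intensity among a patient's occurrences in that period. The sentence also concerns mild, moderate and severe intensity; CTCAE grade is a separate scale for which no maximum rule is given.

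A reader might also infer that DLT or MTD findings are distorted. They are not shown to be. DLTs have their own definition, population and summary; ADRs of grade 2 or higher are listed; the Cohort Review Committee reviews all available data before escalation; and all AEs are listed with TESS flagged.

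**Conclusion.** The point holds in a limited form. The mismatch between the TESS definition and the period rule follows directly from SAP section 6.1.1.2. Provided that a worsening AE is kept as one record, an AE that starts between consent and Day 1 and worsens on drug is lost from the by-period TESS tables, including the serious-TESS table if it becomes serious. On the same assumption, worsening in a later cycle is not shown in that cycle. Whether the peak is then shown in the onset cycle remains open, because the scope of the maximum is undefined.

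The size cannot be put as a number of events. The effect is confined to descriptive by-cycle AE tables for a secondary objective. It is worth correcting because cohorts are small and the SAP is meant to fix these tables before database lock.

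**What to change.** In SAP section 6.1.1.2:

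1. Change the period rule to use the date of onset or, for an AE that worsens in severity or seriousness, the date of worsening. State that pre-dose AEs enter at the date of worsening.
2. Define maximum intensity and maximum CTCAE grade within patient, preferred term and period.
3. State the recording convention. If the eCRF already opens a new record at each worsening, say that this record's start date is the one used; the first change then needs no further programming.
4. If dates of worsening were not captured, add a TESS table pooled over cycles so that these events are still counted, and footnote the by-cycle tables accordingly.

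The cost is a few sentences of SAP text and modest programming. No new eCRF field is needed. No primary endpoint or primary analysis changes, so the condition for a substantial amendment in protocol section 9.5 is not met.
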